### **8.4. Study Size**

There is no pre identified study size. All patients that met the criteria entered for study.

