### **8.6. Data Analysis**

Categorical covariates described by frequency distribution while continuous covariates expressed in terms of their mean and standard deviation or median and interquartile range as appropriate. Patients were divided according to the mean of disease duration groups (below and above mean) and unadjusted comparisons between groups of the covariates and the outcomes are evaluated using chi2 tests for categorical data, while for continuous data, we used the student's t-test for normally distributed variables and the Kruskall-Wallis test for non-parametric data.

We determined the effect of early referral on the biologic treatment response patients with RA a multivariate analysis by using a stepwise linear regression models. The response variable is defined as DAS28 and CDAI at last visit. The baseline variables considered demographic data, disease duration (years), methotrexate (yes/no), Current steroid therapy (yes/no), baseline DAS28 and CDAI, RF positive (yes/no), anti-CCP (yes/no), present smoking (yes/no).

We determined the effect of early response by using the difference between the base line DAS28 and CDAI. P value <0.05 considered statistically significant.

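### Section 8.6 names only equal-variance methods (Student's t-test, ordinary linear regression); its p-values may be miscalibrated if outcome spread varies with disease duration

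*Combined protocol and SAP*

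**What the plan says.** All of the analysis plan is in section 8.6 (Data Analysis).

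- **Grouping.** "Patients were divided according to the mean of disease duration groups (below and above mean"). The cut is the sample mean, not the median or a fixed number of years.
- **Unadjusted comparison of covariates and outcomes.** For continuous data, the plan uses Student's "t-test for normally distributed variables and the Kruskall-Wallis test for non-parametric data". No criterion for judging normality is given.
- **Adjusted analysis.** It is "a multivariate analysis by using a stepwise linear regression models". On the outcome, "The response variable is defined as DAS28 and CDAI at last visit". On the regressors, "The baseline variables considered demographic data, disease duration (years), methotrexate (yes/no") and further items. Duration enters in years; the below/above-mean group is not among the listed variables.
- **Decision rule.** "P value <0.05 considered statistically significant". Sidedness is not stated.

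No Welch test, robust standard error, variance check or residual diagnostic is named. Section 8.4 (Study Size) states: "There is no pre identified study size. All patients that met the criteria entered for study".

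**The concern.** Student's t-test pools the two group variances. Pooling is harmless when the groups are the same size, but a cut at the mean does not secure that. Duration cannot be negative, and section 8.2 sets no upper limit on it, so a right-skewed distribution is a reasonable expectation. More than half the patients would then fall below the mean. If last-visit scores also spread more (or less) in long-standing disease, the pooled standard error is too small (or too large).

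The regression has a related but separate weakness. Duration is used in years, so the mean split plays no part. Ordinary standard errors assume constant residual variance. If residual spread rises with duration, the few patients with very long duration carry both high leverage and the noisiest outcomes, and the standard error of the slope is understated.

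The choice of test by apparent normality adds a third difficulty. DAS28 might be compared on means and CDAI on ranks, leaving the two primary outcomes on different scales and no mean difference for one of them.

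What is at stake is whether the 0.05 threshold means 5% in the analyses on which the early-versus-delayed conclusion rests.

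**Working it through.** The plan has no figure to reproduce: it gives no sample size, power, SD, group sizes or duration distribution. The check is therefore of the mechanism, under stated assumptions.

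**Inputs from section 8.6:** alpha 0.05 (two-sided assumed); two groups cut at the mean; Student's t-test; linear regression on duration in years.

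**Assumed inputs:** the shape of the duration distribution, the SD ratio r = SD above the mean / SD below it, N, and the trend of residual SD with duration.

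**Step 1. Group shares.** For a lognormal variable the share below the mean is p = Φ(√ln(1+CV²)/2).
- CV 0.7: √ln(1.49) = 0.631, p = Φ(0.316) = 0.62.
- CV 1.2: √ln(2.44) = 0.944, p = Φ(0.472) = 0.68.
- A milder skew (gamma, shape 4) gives p = 0.57; an exponential gives 0.63.

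**Step 2. Large-sample type I error of Student's t-test.** With the SD below the mean set to 1, and up to the common factor 1/N:
- true variance of the difference: V_true = 1/p + r²/(1−p)
- pooled variance: V_pool = [p + (1−p)r²] × [1/p + 1/(1−p)]
- type I error = 2 × P(Z > 1.96 × √(V_pool/V_true))

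Example, p = 0.68 and r = 1.5: V_true = 1.471 + 7.031 = 8.502. V_pool = 1.400 × 4.596 = 6.434. √(6.434/8.502) = 0.870, and 1.96 × 0.870 = 1.705, so the error is 8.8%.

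| Share below mean | r = 0.67 (2/3) | r = 1 | r = 1.3 | r = 1.5 |
|---|---|---|---|---|
| 50% | 5.0% | 5.0% | 5.0% | 5.0% |
| 57% | 3.9% | 5.0% | 5.9% | 6.3% |
| 62% | 3.2% | 5.0% | 6.5% | 7.4% |
| 68% | 2.4% | 5.0% | 7.4% | 8.8% |

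**Step 3. Simulation of the group tests (no true difference).** With N = 150, a 65/35 split and r = 1.5, Student gave about 8% and Welch about 5%. Across N = 100 and 300, shares of 50%–69% and r from 0.67 to 2, Student ranged from 2.3% to 12.4% and Welch from 4.7% to 5.4%. The rank test was affected too, but less: 6.1%–6.7% at 63:37 with r = 1.5.

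**Step 4. Simulation of the regression slope.** One regressor (duration), no selection step, true slope zero, N = 200, mean duration 8 years, residual SD = 1 + 0.03 × years (1.06 at 2 years, 1.60 at 20 years).

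| Assumed duration | False positives, ordinary SE |
|---|---|
| Lognormal, CV 0.5 | about 9% |
| Lognormal, CV 0.7 | about 14% |
| Lognormal, CV 0.9 | about 20% |
| Lognormal, CV 0.9, capped at 30 years | about 12% |

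HC3 standard errors gave about 6%–7% in these settings (a repeat run gave 5.4% at CV 0.5). With constant residual SD the ordinary test keeps 5%, and HC3 is at or slightly above it: 5.2%–5.6% with an exponential duration, up to 6%–7% under extreme leverage. If spread falls with duration the ordinary test is conservative: 1.4%–1.7% for SD = 1/(1 + 0.25 × duration/mean), exponential duration.

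**The case against.** The strongest reply is that every harmful ingredient is assumed. The documents do not report that duration is skewed, that the groups are unequal, or that outcome spread changes with duration. A reader might infer that the 0.05 rule certainly fails here, or fails whenever spreads differ. That does not follow: the t-test keeps its level at 50:50 for any SD ratio, and at any split if the SDs are equal. At 57:43 with a ratio of 1.3 the error is only 5.9%, and it can also fall below 5%. This part of the reply stands.

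A reader might also blame the mean split for both analyses. It bears only on the group comparison; the regression lists duration in years. Nor should the 20% be taken as the expected size for the slope. It needs a heavy upper tail, and capping duration at 30 years brings it to about 12%.

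The rank-test branch means that Student's test may never be applied to one or both outcomes. That is correct, but the rank test is not immune to unequal spread, and switching by outcome costs a common effect measure.

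Two further points stand. Stepwise selection distorts the regression p-values whatever standard error is used. And confounding in a retrospective, non-randomised comparison may well matter more than a few points of type I error. Neither is a reason to keep the equal-variance methods when the alternative costs almost nothing.

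**Conclusion.** The point holds conditionally. Section 8.6 commits to equal-variance methods and names no safeguard, so its p-values may be off, in either direction, if outcome spread varies with duration. The size in this study cannot be computed from the documents.

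For the t-test, the 2.4%–8.8% span in the table requires both unequal groups (57%–68% below the mean) and an SD ratio between 0.67 and 1.5. For the slope, the 9%–20% range rests on the assumed SD trend, N and mean duration, varies strongly with the tail of the duration distribution, and describes the test before any stepwise selection. The regression is the more exposed of the two, and it is the analysis from which the plan draws the effect of early referral. The change is worth making because it does not require anyone first to show that the variances differ.

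**What to change.** In section 8.6:

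1. Replace Student's t-test and the normality-driven switch by Welch's t-test for both DAS28 and CDAI at last visit, reporting the mean difference with a 95% CI.
2. Keep the rank test for both outcomes as a sensitivity analysis.
3. Report HC3 standard errors in the linear regressions.
4. Report group sizes and outcome SDs by group, so that readers can see whether the issue was material.

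Section 5 (Milestones) records that the protocol was written after the analysis was completed, so this is a re-analysis of the existing dataset, to be disclosed as such, and not an edit to a future plan. The work is one software option per analysis plus revised tables. The loss of power with equal variances is negligible: one simulation gave 82.0% for Welch against 82.2% for Student. HC3 does not make p-values valid after stepwise selection; that needs a separate correction.

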## 6. RATIONALE AND BACKGROUND

In the past 1–2 decades, treatment paradigms in rheumatoid arthritis (RA) have shifted dramatically from initial treatment with nonsteroidal anti-inflammatory drugs (NSAIDs), followed by cautiously progressive addition of disease-modifying antirheumatic drugs (DMARDs), to the current treatment approach of aggressive initiation of DMARD therapy soon after the diagnosis of RA has been made. This change in RA management results from increasing data supporting improved prognosis and outcomes with the initiation of DMARD therapy early in the course of symptomatic disease. Since the goals in RA management include not only disease remission, but also improved functional status, which is strongly associated with radiographic joint damage, an understanding of the impact that the initiation of appropriate treatment during early RA has on these outcomes is essential.

Accurate diagnosis of early RA begins with clear definitions of RA, as there is considerable variability in the literature regarding the time frame defining early RA. Previous intervention studies in early RA have included early RA as disease duration from 3 months to 3 years; however, with the knowledge of improved outcomes with earlier treatment in RA, it becomes clear that a shorter time interval for classification of early RA is clinically significant. Due to the wide range of definitions of early RA presented in the literature, it is difficult to characterize the specific time frame that defines early RA. However, it is now generally accepted that early RA is the onset of symptoms of joint (typically polyarticular) pain, stiffness, or swelling within the past 3 months, although in practical terms it may be difficult for rheumatologists to evaluate patients within that 3-month time frame, due to a variety of factors, including delay in referral of patients with early symptoms of inflammatory arthritis (IA) or delays in patients seeking medical attention for their symptoms.

Multiple studies have evaluated the benefits of early treatment of RA, including several that have evaluated the impact of early DMARD treatment on successful response to therapy. In particular, a meta-analysis of ~1,400 RA patients from 14 randomized controlled trials identified that one of the strongest predictors of response to therapy was a shorter disease duration at the time of treatment initiation.

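### The only adjusted estimate of early versus delayed start rests on an unchecked straight line in disease duration, which can understate the difference if durations are skewed and the effect lies in early disease

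*Combined protocol and SAP*

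**What the plan says.** Section 8.6 (Data Analysis) describes the adjusted analysis as obtained "by using a stepwise linear regression models". On the outcome it says: "The response variable is defined as DAS28 and CDAI at last visit". On the covariates it says: "The baseline variables considered demographic data, disease duration (years", followed by several items marked yes/no. Disease duration carries only a unit. No log, spline, polynomial, category or linearity check is mentioned anywhere.

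Duration has one other use, in the unadjusted comparisons: "Patients were divided according to the mean of disease duration groups (below and above mean".

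The question is an early-versus-delayed one. Section 7 compares early with delayed start, and the hypothesis in section 8.2 is that response does not differ between early and delayed referral. Section 6 reviews how early RA has been defined ("Previous intervention studies in early RA have included early RA as disease duration from 3 months to 3 years") and adds that "it becomes clear that a shorter time interval for classification of early RA is clinically significant".

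No section gives the mean, spread or skew of disease duration. On sample size, section 8.4 says: "There is no pre identified study size".

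**The concern.** No other listed covariate measures how early treatment began, so the duration coefficient carries the adjusted answer to the research question. A single slope per year assumes that going from 0 to 1 year costs as much as going from 20 to 21 years. It can be read as an early-versus-delayed difference only if that holds, and the plan does not check it.

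A least-squares slope gives most weight to patients far from the mean duration. If durations are right-skewed, those are mainly the longer-duration patients. If the effect is also concentrated in early disease, these patients lie on the flat part of the curve and pull the slope towards zero. The adjusted analysis could then report little effect when an early effect is real. Stepwise selection adds to this, because an attenuated term is more likely to be dropped, leaving no adjusted estimate at all.

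**Working it through.** The plan has no stated sample size, power or effect to reproduce. Everything below about distribution, effect size and N is assumed. From section 8.6 come the linear model, the unit of years and the 0.05 threshold (sidedness not stated; two-sided assumed).

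**1. Smooth early effect**

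- Assumptions: duration d is lognormal with CV 0.9 and mean 6 or 8 years. The outcome is y = 1 − exp(−d/τ) + 0.4 × baseline + error, with residual SD 1.2 and τ = 1.5 or 3 years. Longer duration thus raises the last-visit score by at most 1.0 point.
- True 10-versus-1-year difference = exp(−1/τ) − exp(−10/τ).
  - τ = 1.5: 0.513 − 0.001 = 0.51.
  - τ = 3: 0.717 − 0.036 = 0.68.
- Straight line (9 × slope): 0.07 at mean 8, τ = 1.5, up to 0.27 at mean 6, τ = 3. That is 0.07/0.51 = 14% to 0.27/0.68 = 40% of the truth.
- 3-knot restricted cubic spline: 0.32 to 0.64 in the same scenarios. That is 0.32/0.51 = 63% to 0.64/0.68 = 94%.
- Power at τ = 3, N = 400: line 0.53 to 0.70; spline (2-df test) 0.79 to 0.88.
- Power at τ = 1.5, N = 400: even the spline reaches only about 0.49 (mean 6) and 0.29 (mean 8).

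**2. Same model, mean duration 3 years**

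- Line: 0.51 to 0.57 against a true 0.51 (τ = 1.5), and 0.66 to 0.70 against 0.68 (τ = 3). There is little bias on this contrast.
- Power still differs: 0.69 for the line and 0.87 for the spline at τ = 1.5, N = 400.

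**3. If the truth is linear**

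- With 0.04 points per year, the 10-versus-1-year difference is 9 × 0.04 = 0.36.
- At mean 8, N = 200, power is 0.89 for the line and 0.82 for the spline, a cost of 0.07.

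**4. A different shape: a step at the edge of an early window**

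- The share of a true in-versus-out contrast that a line recovers equals r² between the window indicator and duration.
- Example: gamma durations with mean 8 and SD 7, 2-year window, 16.5% of patients inside, slope −0.0233 per year. The difference in mean duration is 0.0233 × 49 / (0.165 × 0.835) = 8.29 years. The line implies 0.0233 × 8.29 = 0.193 of the true contrast.
- Over eight assumed gamma or lognormal distributions (means 3 to 10 years) the share is:

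| Window | Share recovered by the line |
|---|---|
| 0.25 year | 0.00 to 0.08 |
| 1 year | 0.00 to 0.28 |
| 2 years | 0.03 to 0.47 |
| 3 years | 0.09 to 0.58 |

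- The line misses more than half in 30 of 31 evaluable cases.
- Patients above the mean are 34 to 39% of the sample but supply 70 to 80% of the sum of squares that fixes the slope.

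**5. Does the split at the mean repair this?**

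Not dependably. For gamma mean 8, SD 7 it shows 0.12, 0.27 and 0.42 of the true contrast for 1-, 2- and 3-year windows. It is also unadjusted and tied to no definition of early RA.

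**The case against.** A reader might infer that section 6 claims a benefit confined to the first months or years, so that the linear term contradicts the plan's own rationale. The documents do not support that. The range of 3 months to 3 years is how earlier studies defined early RA; it does not describe where the effect lies. Section 6 states no threshold or plateau, and its discussion concerns starting DMARDs, not etanercept specifically. The meta-analysis it cites found that shorter duration predicts response, which a steady gradient also fits.

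A reader might also infer that the slope *is* driven by a few long-standing patients and *does* miss most of the effect. That cannot be said without the duration distribution and the effect shape, and the documents give neither. At mean 3 years the loss on the 10-versus-1-year contrast nearly vanishes. In the step-window work the dominant patients are about a third of the sample. For gentler curves a line keeps much of the signal: r² is 0.39 to 0.75 for exp(−d/3) and 0.73 to 0.79 for a log gradient.

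Nor is the spline uniquely right. A log term, log(d + 0.25), uses one degree of freedom and had higher power in the curved scenarios (τ = 3, N = 400: 0.92 against 0.87 at mean 6, and 0.84 against 0.79 at mean 8). The spline had less bias, however, and under a linear truth of 0.36 the log term gave 0.55 to 0.72.

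Contrasts against 1 year would be fragile. Under the assumed means of 6 and 8 years, only about 3% and 1% of patients have durations below 1 year. The 10th-percentile knot sits at about 1.7 and 2.2 years, so such contrasts rest on the spline's straight tail.

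Finally, section 5 says the protocol was written after the analysis was complete. A new functional form is therefore a post-results choice.

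These points limit the claim and shape the remedy. They do not remove the gap: the form is linear by default, unchecked, and carries the main question.

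**Conclusion.** The concern holds in conditional form. Section 8.6 leaves disease duration linear by default, makes it only a stepwise candidate, and plans no check, although this term is the only adjusted measure of early versus delayed start. If durations are right-skewed with a mean of 6 to 8 years and the effect decays exponentially, the line recovers roughly 14 to 40% of the difference between 10 and 1 years. At mean 3 years there is little bias on that contrast. Which case applies cannot be told from the documents, so the figures show what could happen; they do not estimate the error in this study. The simulations keep duration in the model and so leave out the further effect of stepwise selection. The change is worth making because it is cheap and covers both a straight and a curved relation.

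**What to change.** In section 8.6:

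1. Report the distribution of disease duration at etanercept start (mean, SD, median, quartiles, and the 10th and 90th percentiles).
2. Keep duration in the model for each outcome rather than leaving it to stepwise selection.
3. Alongside the linear-term model, fit a 3-knot restricted cubic spline with knots at the 10th, 50th and 90th percentiles, and give the 2-df joint test.
4. From the spline, report adjusted mean differences with 95% CI between durations in the well-populated range, for example the 10th, 50th and 90th percentiles.
5. Label this a post hoc sensitivity analysis and report both forms whatever they show.

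The cost is one extra degree of freedom and a re-run on the spreadsheet described in section 8.5. If the relation is truly linear there is a small loss of power, about 7 points in the example above (0.89 to 0.82). The spline will not rescue a sample with few early patients: at mean 8 years and τ = 1.5 it still gave only 0.32 of a true 0.51.

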## 7. RESEARCH QUESTION AND OBJECTIVES

The objective of this study is to see the impact of early initiation of etanercept on patient response compared to delayed introduction of biological treatment.

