## 8. RESEARCH METHODS

### 8.1. Study Design

- **Retrospective analysis** of patients with RA that received etanercept from Baghdad teaching hospital (Rheumatology center) from 2012 until 2018 (inclusion and exclusion criteria will apply for selecting patients).
- **Primary aim:** determine the impact of early referral for management in patients with RA compared to delayed management.
- **Secondary aims:** Determine the influence of early referral on the response to biological treatment.

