### 8.2. Setting

#### Patients and Methods

Data collected from the Baghdad teaching hospital registry. The rheumatology patient registry is a prospective longitudinal multicenter cohort initiated in 2012. It captures all patients treated with biologic therapies managed in the rheumatology department. The decision to initiate and maintain the treatment is guided by the ACR (American College of Rheumatology) recommendations.

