### **8.3. Data Sources**

We identified patients in rheumatology registry with rheumatoid arthritis and obtained information on patient demographics (age, gender), education level (years), present smoking status, disease duration (years), current steroid therapy (yes/no), baseline DAS28 (Disease Activity Index 28) & CDAI (Clinical Disease Activity Index) RF (Rheumatoid factor) status, anticitrullinated protein antibody (anti-CCP) status. Primary Outcomes: Disease activity Index (DAS28) and CDAI in last follow up visit.

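### Disease duration alone cannot show an effect of early referral or early etanercept, because prior conventional DMARD treatment is almost unrecorded

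*Combined protocol and SAP*

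**What the plan says.** The plan describes what it is studying in three ways.

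- Section 6 argues from the timing of DMARD therapy, citing "increasing data supporting improved prognosis and outcomes with the initiation of DMARD therapy early in the course of symptomatic disease". It adds from a meta-analysis that "one of the strongest predictors of response to therapy was a shorter disease duration at the time of treatment initiation".
- Section 7 sets the objective as the "impact of early initiation of etanercept on patient response compared to delayed introduction of biological treatment".
- Section 8.1 gives the primary aim as to "determine the impact of early referral for management in patients with RA compared to delayed management", with the influence of early referral on biologic response as a secondary aim.

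All three rest on one variable. Section 8.6 states: "Patients were divided according to the mean of disease duration groups (below and above mean"). The comparison between these groups is unadjusted. The adjusted analysis is a stepwise linear regression for DAS28 and CDAI at last visit: "The baseline variables considered demographic data, disease duration (years), methotrexate (yes/no"), then current steroids, baseline DAS28 and CDAI, RF, anti-CCP and smoking.

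The data list in section 8.3 includes "present smoking status, disease duration (years), current steroid therapy (yes/no") but no conventional DMARD item, not even methotrexate. Eligibility excludes prior biologics and is silent on prior conventional DMARDs. Section 8.2 says of etanercept: "The decision to initiate and maintain the treatment is guided by the ACR (American College of Rheumatology) recommendations". Section 8.8 names missing data as the only limitation.

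**The concern.** Disease duration measures how long a patient has had RA. It does not measure when the patient was referred, when treatment began, or what was tried before etanercept. Two patients with the same long duration may have had opposite histories: one given DMARDs promptly and moved to etanercept years later, the other referred late and untreated until then. The plan puts both above the mean and treats both as delayed.

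If the earlier drug course bears both on when etanercept is started and on how the patient does afterwards, it is a common cause of exposure and outcome that neither analysis controls. A difference between the duration groups, or its absence, would then be reported as an effect of early referral when it might reflect prior treatment. The study's central conclusion is at stake.

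**Working it through.** The plan gives no sample size, effect size, standard deviation or result on this point, so there is no figure to reproduce. The check sets the sections against each other.

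**1. What would be needed to separate the histories.** Telling prompt DMARD treatment from late referral requires at least one of: date of referral, date of first DMARD, number or duration of prior DMARDs, or reason for moving to etanercept.

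**2. What is listed.**

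| Item | 8.3 data list | 8.6 model |
|---|---|---|
| Disease duration | yes | yes |
| Methotrexate yes/no | no | yes |
| Date of referral | no | no |
| Date of first DMARD | no | no |
| Number or duration of prior DMARDs | no | no |
| Reason for moving to etanercept | no | no |

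Methotrexate yes/no carries no date, duration or response, and the plan does not say whether it means current or past use.

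**3. What each analysis can control.** The group comparison adjusts for nothing. In the regression, stepwise selection may drop methotrexate, the baseline activity scores, or disease duration itself.

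**4. Size.** For a yes/no feature of prior treatment that is left out, the bias in a difference in mean last-visit DAS28 is approximately

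bias ≈ g × d,

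where g is the effect of that feature on last-visit DAS28 and d is the difference in its prevalence between the duration groups. The documents give neither. On assumed values only:

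- g = 0.3 points, d = 20 percentage points: 0.3 × 0.20 = 0.06 points
- g = 1.0 point, d = 50 percentage points: 1.0 × 0.50 = 0.50 points

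The range shows only that the bias may be trivial or not, depending on values the plan does not give. The sign depends on whether the feature marks refractory disease or well-managed disease, so the direction is also open.

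**The case against.** The strongest reply is that section 7 asks about early etanercept against later introduction of a biologic. On that objective, a patient who had DMARDs early and etanercept in year 8 is correctly classed as delayed. This stands, and a reader should not infer that such patients are misclassified under section 7. It does not remove the problem: prior DMARD course can still confound that contrast, and the aims in 8.1 and the regression in 8.6 speak of early referral, which duration does not identify.

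Second, baseline DAS28 and CDAI, steroids and serology are candidate covariates and may capture part of the severity at etanercept start. That is fair. They do not record when treatment began or how many drugs were used, and stepwise selection does not guarantee that they stay.

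Third, the mechanism is inferred. Section 8.2 says that recommendations guide treatment, but not what they require, and no section describes response to earlier drugs. This also stands. It is why the point is worded as open to confounding, not as confounding shown.

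Three stronger readings are tempting and not supported:

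- **That no DMARD history is considered at all.** Methotrexate yes/no is in 8.6.
- **That the bias runs mainly against early starters**, because they include fast DMARD failures. Nothing in the documents supports a direction.
- **That the mixed group simply shrinks a true difference by a calculable share.** That would describe dilution from misclassified exposure, not confounding, and the share and the true difference would both have to be assumed.

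**Conclusion.** The point holds as a limit on what may be concluded. The plan's exposure is disease duration, and beyond a methotrexate flag it lists nothing about prior conventional treatment. Neither analysis can therefore support an effect of early referral or early management, and an effect of early etanercept remains open to confounding by prior DMARD course. The documents allow no estimate of size or direction, and they do not show that the bias is present.

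The conclusion rests on two assumptions. Prior DMARD course must plausibly relate both to time to etanercept and to later disease activity. Disease duration must be measured at etanercept start; 8.3 and 8.6 list it as a baseline variable but do not define its start or reference date.

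**What to change.** **Wording changes, needed in any case**

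- In sections 7, 8.1 and 8.6, restate the conclusion as an association between disease duration and DAS28/CDAI at last visit, and drop the claim of an impact or effect of early referral.
- In 8.8, add possible confounding by prior conventional DMARD treatment, of unknown size and direction.
- Reconcile methotrexate between 8.3 and 8.6, and say whether it means current or past use.

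**If the registry holds date of first DMARD and number of prior DMARDs**, add a sensitivity analysis:

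- Replace total duration by two terms, onset to first DMARD and first DMARD to etanercept.
- Report the duration estimate with and without number of prior DMARDs.
- Force these terms into the model so that stepwise selection cannot remove them.
- Label it post hoc, since section 5 says the protocol was written after the analysis was completed.

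**Cost.** The wording changes take a few sentences and narrow the conclusion. The extra analysis depends on fields that the documents do not show to exist. Number of prior DMARDs may lie partly on the causal path from longer duration to outcome, so the adjusted estimate is not automatically the better one. That is why both should be reported.
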